8. STATISTICAL CONSIDERATIONS

8.1. Statistical and Analytical Plans

Methodology for statistical analyses and summary of the data collected in this study is described here and further detailed in a statistical analysis plan (SAP) which will be maintained by the Sponsor. The SAP may modify what is outlined in the protocol where appropriate; however, any major modifications of the primary endpoint definitions or their analyses will also be reflected in a protocol amendment.

8.2. Analysis Population(s)

The following analysis populations are defined:

Population	Definition
Modified Intent-to-Treat (mITT)	All randomized participants who receive at least one dose of vaccine. Participants will be analyzed according to their randomized arm.
Safety	All randomized participants who receive at least one dose of vaccine. Participants will be analyzed according to the actual study intervention received. The Safety Population will be used for all safety analyses.
Immunogenicity	All randomized participants who received at least one dose of vaccine with at least 1 valid follow-up assessment immunogenicity result. Participants will be analyzed according to the actual study intervention received. The Immunogenicity Population will be used for the phase 1 and 2 immunogenicity analyses.

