3.4.2.1. Primary Endpoints

Humoral Immunogenicity:

- GMT of S-specific and N-specific IgG antibodies against 2019 novel coronavirus tested by ELISA in serum
- GMT of neutralizing antibody

Cellular Immunogenicity:

- T cell activity against SARS-CoV-2 S protein and N protein as assayed by ELISpot

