6.4. Follow-Up for Disease History

Participants will be followed for self-reported SARS-CoV-2 exposure, symptoms of COVID-19 disease, and any outside test results for SARS-CoV-2 infection at study visits. Participants with symptoms of COVID-19 should be encouraged to seek testing and care, if appropriate, from their usual provider.

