8.3.3. Analyses of Immunogenicity

In phase 1 and phase 2, immunogenicity endpoints will be summarized using descriptive statistics for the immunogenicity population. Data will be log-transformed for analyses, as appropriate. GMTs and their associated 95% confidence intervals (CIs) will be computed based by exponentiation of the corresponding log-transformed means and 95% CIs at each time point.

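### The plan neither removes nor separately shows immunogenicity results taken after an intercurrent SARS-CoV-2 infection or a non-study COVID-19 vaccination

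*Combined protocol and SAP*

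**What the plan says.** - **Who is analysed.** Section 8.2 defines the Immunogenicity Population as randomized and dosed participants "with at least 1 valid follow-up assessment immunogenicity result". It does not say what makes a result valid. It adds: "The Immunogenicity Population will be used for the phase 1 and 2 immunogenicity analyses".
- **What is computed.** Under Section 8.3.3, "immunogenicity endpoints will be summarized using descriptive statistics for the immunogenicity population", and GMTs with their 95% CIs "will be computed based by exponentiation of the corresponding log-transformed means and 95% CIs at each time point".
- **Status of the endpoints.** Section 3.4.2.1 lists "GMT of S-specific and N-specific IgG antibodies against 2019 novel coronavirus tested by ELISA in serum" as primary in phase 2, with the neutralizing antibody GMT and T-cell activity by ELISpot. Section 3.4.1.2 makes the same measures secondary in phase 1.
- **Infection data after dosing.** Section 6.4: "Participants will be followed for self-reported SARS-CoV-2 exposure, symptoms of COVID-19 disease, and any outside test results for SARS-CoV-2 infection at study visits". As extracted, Table 10 also shows SARS-CoV-2 swabs at screening, day 1 and about days 22 and 29.
- **Outside vaccination.** Section 4.1.2 bars COVID-19 vaccination, and infection, in the 3 months before enrollment. No rule covers the time after dosing. The only visible route for recording a later vaccination is the general concomitant-medication record in Section 6.8.
- **Inference.** Section 8.3.1 plans no statistical comparison of the phase 2 arms. It mentions subgroup summaries only for the randomization strata, and only as a possibility. Section 8.1 leaves further detail to a SAP; no separate SAP text is among the documents reviewed.

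**The concern.** The immunogenicity summaries are meant to describe the response to the study vaccine. A participant who catches SARS-CoV-2, or is vaccinated elsewhere, between dosing and a blood draw may show a rise that the study vaccine did not cause. The protocol already treats such events as relevant before enrollment: it imposes the 3-month limits and stratifies phase 2 by previous infection (Section 8.5). After dosing it collects infection information but does not connect it to the immunogenicity analysis. A programmer working from Sections 8.2 and 8.3.3 alone would leave post-event results in.

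Three features raise the stakes:

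- In phase 2 these are the primary endpoints, and with no model or comparison planned, the arm summaries are the whole primary result.
- The direction can be perverse. An arm with less protection would have more infections, and those infections would raise its GMT.
- Phase 2 is open-label, so outside vaccination could differ between arms for reasons other than chance.

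**Working it through.** **1. Plan figures.** Section 8.4 gives 6 × 10 = 60 in phase 1 and 4 × 30 = 120 in phase 2. These sum to the 180 in Section 3.2. The sizes have no statistical justification, so there is no power figure to reproduce.

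**2. Which draws are exposed.** As extracted, Table 10 shows immunogenicity blood on day 1 (before dosing), day 8 and one late visit.

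- The late mark falls in the day 180 column.
- In the same block, the late pregnancy-test mark falls in the day 36 column, while footnote m places that test at day 29. That is a shift of one column. The same shift would put the late immunogenicity draw at day 60.
- The table lists telephone follow-up at days 180 and 365, which also favours day 60. It still numbers day 180 as a clinic visit, so the point stays open.

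Time at risk from day 1 is 7 days at the day 8 draw, and 59 or 179 days at the late draw. Experimental arm 3 is dosed again on day 29, so the late draw is its only result after the second dose, 31 or 151 days later.

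**3. Effect on a GMT.** A GMT is the exponential of the mean log titre. If a fraction f of an arm has titres raised k-fold by an event, the mean log rises by f × ln k, so the GMT is multiplied by k^f. Here f and k are assumptions; the documents give neither.

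| Events in 30 | f | k = 4 | k = 10 |
|---|---|---|---|
| 1 | 0.033 | 1.05 | 1.08 |
| 3 | 0.10 | 4^0.10 = 1.15 | 10^0.10 = 1.26 |
| 6 | 0.20 | 4^0.20 = 1.32 | 10^0.20 = 1.58 |

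In a phase 1 cohort of 10, a single event gives f = 0.10 and so the same 1.15 to 1.26. The formula is for geometric means. Section 8.3.3 log-transforms only where appropriate, so I do not apply it to ELISpot; the direction there is the same.

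**4. How often this could arise.** With an assumed per-person risk p by the late draw, the chance of at least one event among 30 is 1 − (1 − p)^30. The chance that two arms of 30 with equal risk differ by three or more events comes from two independent binomials.

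| p | At least 1 of 30 | Two arms differ by 3 or more |
|---|---|---|
| 5% | 78.5% | 13% |
| 10% | 95.8% | 28% |
| 20% | 99.9% | 42% |

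An excess of three events in one arm gives an apparent GMT ratio of 1.15 (k = 4) to 1.26 (k = 10) when the true ratio is 1.

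**5. Scale against sampling error.** For n = 30 the 95% CI factor is 10^(t × SD/√30), with t = 2.045 on 29 degrees of freedom. For an assumed log10 SD of 0.3 to 0.6 this is 1.29 to 1.68. A shift of 1.15 to 1.26 therefore lies inside the CI half-width, but near it at the low end of the SD range. The CI would not reveal the shift as bias.

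**The case against.** **The omission is silence, not a rule.** A reader might infer that the protocol says every follow-up titre counts, including those after infection. It does not. The population definition in Section 8.2 selects participants, not results. *Valid* is undefined, and a SAP definition could carve these results out. This stands. The supportable statement is that the text reviewed applies no exclusion and plans no separate display, so following it literally keeps the results in.

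**The exposure may be short.** A reader might take the late draw to be six months out. Table 10 does not establish that: day 60 is at least as well supported, and the day 8 draw leaves little time for an event. This stands, and it makes the 20% scenario less plausible.

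**The size is assumed and modest.** Even the 1.26 needs three events in 30, each with a full 10-fold rise on top of a recent boost. No test or decision rule is distorted, so an inference that type I error is inflated would be wrong. This also stands.

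**Exclusion can bias too.** A reader might conclude that post-event results should be dropped from the main summary. The documents do not support that preference. An all-results summary is a legitimate treatment-policy description. Dropping results conditions on a post-randomization event that vaccination may affect. Detection is also incomplete: swabs appear to end near day 29, and later infections rest on self-report and outside tests in an open-label trial. This is the strongest point. It argues for showing both summaries, not for leaving one out.

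**Conclusion.** The concern holds in limited form. Sections 8.2 and 8.3.3, followed as written, mix results taken after an intercurrent infection or outside vaccination into the phase 2 primary summaries, and nothing in the text reviewed lets a reader see how far. The late draw carries most of the risk.

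The illustrative size is a GMT multiplied by 1.15 to 1.26 for 3 of 30 participants with a 4- to 10-fold rise. It rests entirely on assumed event counts and fold-rises. The multiplier compares the arm with what the same 30 people would have shown without the event. Dropping the results recovers that value only if those participants would otherwise have responded like the rest.

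The consequence is a descriptive GMT or ELISpot summary that may be misread as vaccine response. This is a cheap improvement to the plan, not a flaw that invalidates it.

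**What to change.** In Section 8.3.3:

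1. Keep the all-results GMT and ELISpot summaries.
2. Add a prespecified parallel set that drops results collected after a positive study PCR, a reported positive outside test or a recorded non-study COVID-19 vaccination.
3. Report the number of results dropped, by arm (cohort in phase 1) and time point.
4. State as a limitation that swabs appear to end near day 29, that later infections depend on self-report and outside tests in an open-label trial, and that silent infections will stay in both summaries.

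In Section 8.2, define what makes a result valid. In the CRF, add an explicit item for COVID-19 vaccination outside the study, because footnote c of Table 10 covers exposure, symptoms and outside tests but not vaccination. Fix the rule before results are seen.

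The cost is a few sentences, one CRF item and one extra table set. The parallel summary has slightly wider CIs: with 3 of 30 dropped and the same SD, the interval on the log scale widens by about √(30/27) = 1.05. Sample sizes do not change.

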8.3. Statistical Methods

8.3.1. General Approach

The purpose of this phase 1/2 study is to determine the safety, reactogenicity, and immunogenicity of saRNA COVID-19 boost vaccines in participants that have been previously vaccinated against or previously infected with COVID-19. Participants enrolled will include individuals previously vaccinated against COVID-19 or previously infected with COVID-19 > 3 months prior to enrollment. The phase 1 study is a single arm, open-label study. The phase 2 is a randomized open-label study. For the phase 2 study, laboratory analyses of immunogenicity assessments will be performed blind to participants' vaccine treatment on study. Results for phase 1 will be summarized by cohort and results for phase 2 will be summarized for each randomized arm.

Descriptive statistics will be presented for all study endpoints. Continuous variables will be summarized as mean, median, standard deviation, and minimum and maximum values.

Categorical variables will be summarized as the number and percentage of participants in each category. Data from all investigational sites will be pooled in the analyses and summary tables.

No statistical comparisons of the phase 2 arms is planned. Subgroup analyses providing descriptive statistics for the various randomization strata levels may be performed depending on the number of participant's in each strata. Details of the subgroup analyses will be provided in the Statistical Analysis Plan.

Data for participants who are screen failures will not be included in the study database or in any analyses or summary tables.

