Solicited local and systemic reactogenicity AEs will be collected using diaries for 7 days following study intervention (ie, administration of vaccine). Unsolicited AEs will be recorded in a diary from time of vaccination until 30 days after study intervention. Medically attended adverse events (MAAEs) and SAEs will be recorded for 6 months after study intervention (related MAAEs and SAEs will be recorded at any time).

Immunogenicity analyses will be conducted by collecting serum and PBMC samples from individual participants before and after vaccinations to test for humoral- and cell-mediated immune responses. Neutralizing antibodies will be assessed.

Phase 2

In the phase 2 study, up to 120 previously vaccinated/infected additional participants will be enrolled. Participants in phase 2 will be randomized 1:1:1:1 to receive Janssen or Pfizer-BioNTech vaccine (control arm), the AAHI SC2 vaccine (experimental arm 1), or the AAHI-SC3 vaccine (experimental arms 2 and 3). Dose levels for the AAHI-SC2 and AAHI-SC3 vaccines will be as determined in the phase 1 study. Randomization will be stratified by age (18 to 55 years or > 55 years), by previous infection (previously infected or not), and by HIV status (positive or negative). Treatment arms are shown in Table 5.

Table 5: Phase 2 Previously Vaccinated/Infected Dosing Schedule

Treatment Arm	Participants	Vaccine	Dosing schedule	Dosage
Control arm	30	EUA or approved vaccine	Day 1	Per prescribing information
Experimental arm 1	30	AAHI-SC2	Day 1	TBD: As determined in phase 1 study
Experimental arm 2	30	AAHI-SC3	Day 1	TBD: As determined in phase 1 study
Experimental arm 3	30	AAHI-SC3	Day 1 and day 29	TBD: As determined in phase 1 study

In addition to dosing visits described above, all participants in all phases of the study will have follow up study visits for data collection.

The SRC will provide ongoing safety review in the phase 2 study. If a possible safety signal is detected, the SRC will determine if the event warrants stopping the trial, modifying the trial, or continuing without modification.

Solicited local and systemic reactogenicity AEs will be collected using diaries for 7 days following study intervention (ie, administration of vaccine). Unsolicited AEs will be recorded in

a diary from time of vaccination until 30 days after study intervention. MAAEs and SAEs will be recorded for 6 months after study intervention (related MAAEs and SAEs will be recorded at any time).

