3.3. Duration of Study

3.3.1. Duration of Treatment

For most participants, treatment will be confined to study day 1. For participants in experimental arm 3 of the phase 2 study, treatment will occur on day 1 and day 29.

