8.4. Sample Size

The sample sizes for phases 1 and 2 are not based on statistical justification. A total of 60 participants will be treated in phase 1 (10 participants for each cohort). A total of 120 participants will be randomized in phase 2 to receive either the control arm or one of the experimental arms (30 participants/arm).

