8.5. Randomization

In the phase 2, 30 participants will be randomly assigned to each arm based a 1:1:1:1 randomization ratio. The phase 2 randomization will be stratified by age (18 to 55 years or > 55 years), by previous infection (previously infected or not), and by HIV status (positive or negative). The randomization for the phase 2 portion of the study will be performed by site personnel through the study EDC system.

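### If phase 2 arms 2 and 3 share one AAHI-SC3 dose, a combined summary up to the second dose would use up to 60 participants instead of 30, but section 8.3.1 describes by-arm summaries only

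*Combined protocol and SAP*

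**What the plan says.** Table 5 in section 3.1 assigns AAHI-SC3 on day 1 to experimental arms 2 and 3. Section 3.3.1 gives the only scheduled difference: "For participants in experimental arm 3 of the phase 2 study, treatment will occur on day 1 and day 29". On dose, section 3.1 says "Dose levels for the AAHI-SC2 and AAHI-SC3 vaccines will be as determined in the phase 1 study". Table 5 marks each arm's dose as still to be determined and does not say that the two arms will use the same one.

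Section 8.5 states that "30 participants will be randomly assigned to each arm based a 1:1:1:1 randomization ratio", stratified by age, previous infection and HIV status.

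On reporting, section 8.3.1 says that "results for phase 2 will be summarized for each randomized arm", and adds that "No statistical comparisons of the phase 2 arms is planned". It provides for pooling across sites and for possible subgroup summaries by stratum, but mentions no combined AAHI-SC3 summary. Section 8.2 analyses the Safety and Immunogenicity populations by the intervention actually received. Section 8.3.3 reports GMTs with 95% confidence intervals at each time point.

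In section 3.4.2.2.1 only solicited AEs are counted after each vaccination. MAAEs, SAEs and unsolicited AEs are counted from the final vaccination.

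**The concern.** With a common dose, nothing in the assigned treatment separates arms 2 and 3 before day 29. Randomization within the same strata makes them two samples of one treatment group. Reporting them only side by side bases each estimate of the response to a first AAHI-SC3 dose on half of the participants who can inform it.

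Precision is most of what this phase delivers. Section 8.4 says "The sample sizes for phases 1 and 2 are not based on statistical justification", and no arm comparison is planned, so the output is rates, GMTs and their intervals. GMTs are phase 2 primary endpoints (section 3.4.2.1).

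By-arm tables alone also invite over-reading. Two identically treated groups of 30 will differ by chance, and without a combined column a reader may take such a difference as real.

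**Working it through.** **The plan's own figures.** 4 arms × 30 = 120, which matches section 8.4: "A total of 120 participants will be randomized in phase 2". With phase 1, 60 + 120 = 180, which matches section 3.2. There is no power or precision figure to reproduce.

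**Inputs.** n = 30 per arm (section 8.5), so arms 2 and 3 together give at most 60. The documents give no event rates and no titre SD. Those below are assumptions, shown over a range.

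**Zero events observed.** The exact two-sided 95% upper limit is 1 − 0.025^(1/n).
- n = 30: 11.6%
- n = 60: 6.0%

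**Chance of seeing an event at least once.** 1 − (1 − p)^n.

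| True risk p | n = 30 | n = 60 |
|---|---|---|
| 1% | 26% | 45% |
| 2% | 45% | 70% |
| 3% | 60% | 84% |
| 5% | 79% | 95% |

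**Common reactions.** At an observed rate of 20%, the exact 95% interval is 7.7% to 38.6% for 6/30 and 10.8% to 32.3% for 12/60.

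**Chance difference between two identical groups of 30.** At a true incidence of 50%, 1.96 × √(2 × 0.25/30) = 0.253. Differences of up to about 25 percentage points are therefore compatible with no difference at all.

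**GMT interval.** The multiplicative factor is 10^(t × SD/√n), where t is the 97.5% point on n − 1 degrees of freedom.

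| Assumed log10 SD | n = 30 | n = 60 |
|---|---|---|
| 0.4 | 1.41 | 1.27 |
| 0.5 | 1.54 | 1.35 |
| 0.6 | 1.68 | 1.43 |

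On the log scale the interval is about 31% narrower whatever the SD, because the ratio of t/√n at n = 60 to that at n = 30 is 0.692.

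**Sixty is a maximum.** Randomized participants are not replaced (section 4.6), and the Immunogenicity population needs a valid follow-up result (section 8.2). If 10% were missing in each arm (an assumption), the zero-event limits would be 1 − 0.025^(1/27) = 12.8% and 1 − 0.025^(1/54) = 6.6%. The relative gain is almost unchanged.

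**Which data qualify.**
- Solicited AEs in the 7 days after dose 1 can be combined directly.
- MAAEs, SAEs and unsolicited AEs run from the final dose, which is day 29 in arm 3, and a 30-day window from day 1 would cross day 29. They need a new cut-off at the second dose.
- Immunogenicity samples qualify if drawn before the second dose. As Table 10 is extracted, that means the day 1 baseline and day 8. Its columns are visibly shifted in places, so the visit should be checked against the intact table.
- For day 29, Table 10 requires collection before vaccination for urinalysis. Its notes on chemistry, hematology and vital signs set no such order.

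**The case against.** The strongest reply is that nothing is lost. Both arms will be reported, incidence counts can be added by any reader, and no test, precision target or decision rule depends on having 60. Section 8.1 also leaves detail to a separate SAP whose text is not among the supplied documents, so silence in section 8.3.1 does not exclude a combined table.

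Part of this stands: the loss is one of presentation and precision, and a combined column may yet appear. But GMT intervals cannot be combined as simply as counts. In an open-label trial it is also better to fix the grouping before data are seen. The rule in section 8.2 of analysing by intervention received points the same way, since before day 29 that intervention would be identical in the two arms.

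A reader might infer more than the documents support:
- **That the arms certainly receive the same treatment.** One dose per product is the natural reading, but it is never stated.
- **That every dose-1 safety rate is affected.** Only solicited AEs are tied to each dose.
- **That all day-29 laboratory values and vital signs are pre-dose.** This is not required.
- **That a day-8 titre is itself the primary endpoint.** Section 3.4.2.1 names no time point.
- **That the combined column should become the main estimate.** The gain does not depend on that, and section 8.1 calls for a protocol amendment for major changes to primary endpoint analyses.

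Finally, arm 3 participants know that a second dose is coming, so their diary reporting could differ slightly. That is a reason to keep the by-arm columns, not to omit the combined one.

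**Conclusion.** The point holds conditionally, as a cheap improvement. If arms 2 and 3 use one AAHI-SC3 dose, they are exchangeable until arm 3's second dose, and the supplied text describes no summary that uses this. For dose-1 solicited AEs and for immunogenicity samples drawn before the second dose, a combined summary would nearly halve the zero-event upper limit and narrow the log-scale GMT interval by about 31%.

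The conclusion rests on a common dose, on few missing data, and on early samples being taken before the second dose. The GMT factors also rest on the assumed SD. With no between-arm testing planned, combining the arms carries no type I error cost. The by-arm analysis remains valid as it stands.

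**What to change.** State in section 3.1 whether arms 2 and 3 will use the same AAHI-SC3 dose. Then add to section 8.3.1:

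> If the AAHI-SC3 dose is the same in arms 2 and 3, solicited AEs after dose 1, other AEs with onset before the day-29 dose (in arm 2, before the day-29 visit), and immunogenicity results from samples collected before that dose will also be presented for arms 2 and 3 combined, alongside the by-arm summaries. Later data will be presented by arm. Day-29 laboratory values and vital signs will be included in the combined summary only where they were taken before the dose.

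The arm 2 clause is needed because that arm has no second dose to define the cut-off. The same edit should say how section 8.2's grouping by intervention received fits with section 8.3.1's grouping by randomized arm.

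The cost is one extra column in existing tables and one new AE cut-off for events otherwise counted from the final dose. No participants, visits or samples are added. Any difference in open-label diary reporting would show in the retained by-arm columns.

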3.2. Number of Participants

Initially up to 180 participants will be enrolled in this study (60 participants in phase 1, and 120 participants in phase 2).

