3.4.1.1. Primary Endpoints

- Incidence of MAAEs and SAEs through 1 week post final vaccine administration
- Incidence of MAAEs and SAEs through 30 days post final vaccine administration
- Incidence of MAAEs and SAEs through 6 months post final vaccine administration
- Incidence and severity of solicited local reactogenicity AEs through 1 week after each vaccine administration
- Incidence and severity of solicited systemic reactogenicity AEs through 1 week after each vaccine administration
- Incidence and severity of unsolicited AEs through 1 week post final vaccine administration

- Incidence and severity of unsolicited AEs through 30 days post final vaccine administration
- Incidence of abnormal changes of laboratory safety examinations
- Changes in vital signs

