8.3.2. Analyses of Safety

Safety analyses will be summarized with descriptive statistics and performed on the Safety population.

For all phases, safety will be assessed by the incidence of treatment-emergent MAAEs, SAEs, solicited local and systemic reactogenicity AEs, and unsolicited AEs for the time period of interest, overall and by grade according to the Guidance for Industry: Toxicity Grading Scale for Healthy Adult and Adolescent Volunteers Enrolled in Preventive Vaccine Clinical Trials (2007). Clinically significant changes in safety laboratory tests and vital signs will be summarized.

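### Safety incidences, which are most of the phase 1 primary endpoints, are tabulated as number and percentage per cohort of 10 or arm of 30 with no confidence interval specified

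*Combined protocol and SAP*

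**What the plan says.** Section 3.4.1.1 lists nine phase 1 primary endpoints. Eight are incidences of safety events, for example "Incidence of MAAEs and SAEs through 1 week post final vaccine administration"; the ninth is changes in vital signs. All five phase 2 secondary safety endpoints in Section 3.4.2.2.1 are incidences too.

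The analysis is set out in three places:

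- Section 8.3.1, on categorical data: "Categorical variables will be summarized as the number and percentage of participants in each category". It also says that results are presented by cohort in phase 1 and by randomised arm in phase 2. The only pooling it mentions is across investigational sites.
- Section 8.3.2: "Safety analyses will be summarized with descriptive statistics and performed on the Safety population". Incidences are to be given overall and by grade. No interval is named.
- Section 8.3.3, on immunogenicity: "GMTs and their associated 95% confidence intervals (CIs) will be computed". This is the only interval in Section 8.

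On size, Section 8.4 states that "The sample sizes for phases 1 and 2 are not based on statistical justification". Section 8.1 refers to a separate SAP for further detail.

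**The concern.** Section 8.3.1 plans no statistical comparison of the phase 2 arms, and the sample sizes have no statistical basis. Estimation is therefore the whole analysis, and an estimate from 10 or 30 people needs its precision beside it. As written, phase 1 attaches uncertainty to a secondary endpoint (titres) and not to the incidences that make up most of its primary endpoints.

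Two things are lost. The report would not state which event rates the data leave open when a cohort or arm shows few or no events. It would also not state the tighter limit available from everyone who received a given product, because no table combines cohorts, doses or phases.

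**Working it through.** **Inputs.** Section 8.4: "A total of 60 participants will be treated in phase 1 (10 participants for each cohort", in six cohorts per Table 4. Section 8.5: "30 participants will be randomly assigned to each arm based a 1:1:1:1 randomization ratio", with four arms per Table 5. The confidence level for safety is not given, so I assume two-sided 95%, the level used for titres.

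**The plan's own figures.** 6 × 10 = 60; 4 × 30 = 120; 60 + 120 = 180. These agree with Sections 3.2 and 8.4. There is no power or precision figure to reproduce.

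**Denominators at full enrolment.**
- AAHI-SC2: 3 × 10 + 30 = 60.
- AAHI-SC3: 3 × 10 + 2 × 30 = 90, or 60 without experimental arm 3.
- Any saRNA vaccine: 60 + 90 = 150, or 120 without experimental arm 3.

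**Formula.** Exact (Clopper-Pearson) limits for x events in n:
- lower limit = 0.025 quantile of Beta(x, n − x + 1), or 0 if x = 0;
- upper limit = 0.975 quantile of Beta(x + 1, n − x).

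For x = 0 the upper limit reduces to 1 − 0.025^(1/n). With n = 10: 1 − 0.025^(0.1) = 0.3085. With n = 30: 1 − 0.025^(1/30) = 0.1157.

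| Events / n | Group | Exact 95% interval |
|---|---|---|
| 0/10 | one phase 1 cohort | 0 to 30.8% |
| 1/10 | one phase 1 cohort | 0.3 to 44.5% |
| 2/10 | one phase 1 cohort | 2.5 to 55.6% |
| 3/10 | one phase 1 cohort | 6.7 to 65.2% |
| 0/30 | one phase 2 arm | 0 to 11.6% |
| 0/60 | AAHI-SC2, or AAHI-SC3 without arm 3 | 0 to 6.0% |
| 0/90 | AAHI-SC3 | 0 to 4.0% |
| 0/120 | any saRNA vaccine without arm 3 | 0 to 3.0% |
| 0/150 | any saRNA vaccine | 0 to 2.4% |

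**Sensitivity to method.** For 0/10 the upper limit is 30.0% by the rule of three, 27.8% by Wilson and 25.9% by a one-sided 95% exact bound. The range is 25.9% to 30.8%, so the message does not depend on the choice.

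**Chance of seeing at least one event**, 1 − (1 − p)^n. At a true rate of 5% it is 1 − 0.95^10 = 40.1% for a cohort of 10 and 78.5% for an arm of 30. At 10% it is 65.1% and 95.8%.

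**Which pooled denominator fits which window.** Experimental arm 3 is dosed again on day 29. Events before that second dose, including solicited events in the week after dose 1, can use all 150. The 30-day and 6-month windows extend past day 29 when counted from a first dose, so for those arm 3 must be left out and 120 applies.

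**The case against.** **The separate SAP may already do this.** Intervals and integrated tables are the kind of detail Section 8.1 leaves to it. Section 8.3.3 also uses the term descriptive statistics and then includes intervals, so the same term in Section 8.3.2 does not exclude them. This stands as a condition on the point: the text supplied does not provide intervals, but it does not rule them out.

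**The phase 2 dose.** A reader might infer that the dose choice rests on these bare percentages. The documents do not support that. Section 3.1 says the dose levels come from phase 1 but gives no percentage criterion. The safety decisions in Sections 7.8.2 and 7.8.2.1 run through committee review triggered by counts of events, and an interval in a final table changes none of them.

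**Zero of 10.** A reader might also infer that such a result will be taken as absence of risk. That is speculation: the number is reported with the percentage, the cohort size is stated, and the plan claims no precision.

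**The pooled figure.** The 2.4% limit mixes two products, four phase 1 dose levels, undetermined phase 2 doses, and randomised with non-randomised people. It is not a bound for any one product or dose. It also assumes full enrolment, although the numbers are maxima and phase 1 may close early. All of this stands, and it is why the pooled display can only be secondary.

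**The population definition.** Section 8.2 limits the Safety population to randomised participants, while Section 8.3.1 describes phase 1 as single arm. Read literally, phase 1 falls outside the safety denominator. This stands and has to be corrected alongside.

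**Conclusion.** The point holds as an improvement in reporting. On the text supplied, most of the phase 1 primary endpoints and all the phase 2 secondary safety endpoints get number and percentage by cohort or arm, with no interval. The unstated upper limit after zero events is 30.8% for 10 people and 11.6% for 30. Pooling by product would lower it to 6.0% (AAHI-SC2) and 4.0% (AAHI-SC3 before any second dose).

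This rests on a two-sided 95% level, full enrolment for the pooled figures, and a separate SAP that does not already specify intervals. It affects what the trial can report. It does not call into question the trial's conduct, sample size or validity.

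**What to change.** 1. In Sections 8.3.1 and 8.3.2, or in the SAP if not already there, specify Clopper-Pearson 95% intervals for each primary and secondary safety incidence (any event, Grade 3 or higher, SAE, MAAE), by cohort and by arm.
2. As a secondary descriptive display, add a column pooled by product beside the by-dose columns, labelled as pooled over doses and phases. Restrict it to events before any second dose (day 29 in experimental arm 3), or leave that arm out for the 30-day and 6-month windows.
3. If all saRNA recipients are also pooled, label the column as mixing products and doses, and state which denominator applies (150, or 120 without arm 3, at full enrolment).
4. Reword the Safety population in Section 8.2 so that vaccinated, non-randomised phase 1 participants are included.

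The cost is a few sentences and some extra table columns, with no new data and no change in sample size. The downside is that the reported safety estimates will look less certain.
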